6.6 Additional treatment guidance

6.6.1 Treatment compliance

The investigator must promote compliance by informing the participant that compliance is necessary for the participant's safety and the validity of the study. The investigator should also instruct the participant to adhere closely to the scheduled study visits. Study treatment will not be dispensed to the participant but will be administered at designated study visits at the study site by qualified personnel, facilitating compliance. Study drug dosing information should be captured within each designated visit on an appropriate eCRF. The investigator or designee must also maintain an inventory record of study drug (inclisiran/placebo) received and administered.

6.6.2 Recommended treatment of adverse events

Adverse events should be treated according to local practice and guidelines, and is at the discretion of the investigator and treating physician.

For participants with injection site reaction, antihistamines, local or systemic steroids can be used at the investigator's discretion depending on the severity of the reaction.

Medication used to treat AEs must be recorded on appropriate eCRF page(s).

6.6.3 Emergency breaking of assigned treatment code

Emergency code breaks must only be undertaken when it is required to in order to treat the participant safely. Blinding codes may also be broken after a participant discontinues treatment due to disease progression if deemed essential to allow the investigator to select the participant's next treatment regimen, and after discussion and agreement with the sponsor. Most often, study treatment discontinuation and knowledge of the possible treatment assignments are sufficient to treat a study participant who presents with an emergency condition. Emergency treatment code breaks are performed using the IRT. When the investigator contacts the system to break a treatment code for a participant, he/she must provide the requested participant identifying information and confirm the necessity to break the treatment code for the participant. The investigator will then receive details of the investigational drug treatment for the specified participant and a fax or email confirming this information. The system will automatically inform the Novartis monitor for the site and the study team that the code has been broken.

It is the investigator's responsibility to ensure that there is a dependable procedure in place to allow access to the IRT/code break cards at any time in case of emergency. The investigator will provide:

- protocol number
- name
- participant number

In addition, oral and written information to the participant must be provided on how to contact his/her backup in cases of emergency, or when he/she is unavailable, to ensure that un-blinding can be performed at any time.

After an emergency un-blinding, study drug should be permanently discontinued. The participant will continue to be followed up in the study unless informed consent is withdrawn ([Section 9.1.1](#) and [Section 9.1.2](#)).

6.7 Preparation and dispensation

Each study site will be supplied with study drug in packaging as described under investigational and control drugs section.

A unique medication number is printed on the study medication label.

Investigator staff will identify the study medication kits to administer to the participant by contacting the IRT and obtaining the medication number(s). The study medication has a 2-part label (base plus tear-off label); immediately before using the medication kit, site personnel will detach the outer part of the label from the packaging and affix it to the source document.

6.7.1 Handling of study treatment and additional treatment

6.7.1.1 Handling of study treatment

Study treatment must be received by a designated person at the study site, handled and stored safely and properly and kept in a secured location to which only the investigator and designated site personnel have access. Upon receipt, all study treatment must be stored according to the instructions specified on the labels.

Clinical supplies are to be dispensed only in accordance with the protocol. Technical complaints are to be reported to the respective Novartis Country Organization Quality Assurance.

Medication labels will be in the local language and comply with the legal requirements of each country. They will include storage conditions for the study treatment but no information about the participant except for the medication number.

The investigator must maintain an accurate record of the shipment and dispensing of study treatment in a drug accountability log. Monitoring of drug accountability will be performed by monitors during site visits or remotely and at the completion of the trial.

At the conclusion of the study, and as appropriate during the course of the study, the investigator will return all unused study treatment, packaging, drug labels, and a copy of the completed drug accountability log to the Novartis monitor or to the Novartis address provided in the investigator folder at each site.

6.7.2 Instruction for prescribing and taking study treatment

Investigational and control drugs will not be dispensed to the participants. Study drug injections will be performed exclusively at the study site by qualified clinical study site staff under the supervision of the investigator or designee.

The site of injection is the abdomen, alternating sides for each injection. Injections should not be done into areas of active skin disease or injury such as sunburns, skin rashes, inflammation, tattoos or skin infections.

Participants will be administered one s.c. injection of study drug at pre-defined visits as specified in the Assessment Schedule ([Table 8-1](#)) and summarized below.

- **Part 1:** Each participant will receive one injection of blinded inclisiran or placebo on Day 1, a second injection of blinded inclisiran or placebo on Day 90 and a subsequent injection of blinded inclisiran or placebo on Day 270 (“6 months dosing”).
- **Part 2:** Participants randomized to placebo in Part 1 will receive a single injection of blinded inclisiran on Day 360, while participants randomized to inclisiran in Part 1 will receive a single injection of blinded placebo on Day 360. All participants will receive subsequent doses of open-label inclisiran on Day 450 and Day 630.

Injections will be administered after all other study assessments have been completed for the visit. At the Randomization (Day 1) and Day 360 visits, vital signs (blood pressure and pulse) and ADA (Day 1 only) will be assessed a second time 4 hours after injection

Participants must be observed in the clinic for at least 4 hours post injection on Day 1 and Day 360 (i.e. first dosing of inclisiran) and for at least 30 minutes post injection for all other dosing visits before being discharged.

Should a participant develop signs or symptoms of anaphylaxis when study drug is injected, the investigator will need to collect a blood sample for tryptase within 30 minutes of the onset of anaphylaxis (or as soon as possible).

All kits of study treatment assigned by the IRT will be recorded in the IRT system.

All injections to the participant as well as study drug interruptions/discontinuations (i.e. no injection at a designated dosing visit) during the study must be recorded on an appropriate eCRF.

7 Informed consent procedures

Eligible participants may only be included in the study after the participant's parent(s)/legal representative(s) or the participant (if applicable) provides (witnessed, where required by law or regulation), Institutional Review Board (IRB)/Independent Ethics Committee (IEC)-approved informed consent.

In cases where the participant's parent(s)/legal representative(s) give consent, the participant must be informed about the study to the extent possible given his/her understanding. If the participant is capable of doing so, he/she should indicate assent by personally signing and dating the written informed consent document or a separate assent form (as per local requirements). An informed consent must be obtained from the participant once he/she reaches the local legal age of adulthood during the study.

Informed consent must be obtained before conducting any study-specific procedures (e.g. all of the procedures described in the protocol). The process of obtaining informed consent and participant assent where applicable must be documented in the participant's source documents.

Novartis will provide to investigators in separate documents proposed ICF(s) and age appropriate assent form(s) that comply with the International Council for Harmonisation (ICH) Good Clinical Practice (GCP) guidelines and regulatory requirements and are considered appropriate for this study. Any changes to the proposed consent/assent forms suggested by the investigator must be agreed by Novartis before submission to the IRB/IEC.

Information about common side effects already known about the investigational drug can be found in the IB. This information will be included in the informed consent and should be discussed with the participant's parent(s)/legal representative(s) and, to the extent possible, the participant during the study as needed. Any new information regarding the safety profile of the investigational drug that is identified between IB updates will be communicated as appropriate, for example, via an investigator notification or an aggregate safety finding. New information might require an update to the informed consent/assent and then must be discussed with the participant's parent(s)/legal representative(s) and, to the extent possible, the participant.

Women of child bearing potential and her parent(s)/legal representative(s) must be informed that taking the study treatment may involve unknown risks to the fetus if pregnancy were to occur during the study and agree that in order to participate in the study they must adhere to the contraception requirements.

8 Visit schedule and assessments

The Assessment Schedule ([Table 8-1](#)) lists all of the assessments when they are performed. All data obtained from these assessments must be supported in the participant's source documentation.

Participants should be seen for all visits/assessments as outlined in the Assessment Schedule or as close to the designated day/time as possible. Missed or rescheduled visits should not lead to automatic discontinuation.

Participants who prematurely and permanently discontinue from study treatment will continue to be followed up in the study according to the Assessment Schedule unless informed consent is withdrawn.

Participants who prematurely discontinue the study for any reason [e.g. if a participant's parent(s)/legal representative(s) / a participant (if applicable) decide to prematurely and permanently discontinue the participant from study treatment and decline further follow-up visits] should be scheduled for an EOS visit as soon as possible. At this final visit, AEs and concomitant medications should be recorded in the corresponding eCRFs.

Participants will have to comply with the following restrictions:

- Participants should have fasted for at least 8 hours for all visits for fasting lipids/lipoproteins/PCSK9 and glucose blood samples (if the participant has not fasted, the collection of laboratory evaluations must be rescheduled)
- Participants must refrain from unaccustomed strenuous physical exercise for 48 hours before the screening and any study visit until the follow-up has been completed
- Blood donation will not be allowed at any time during the study

If an extraordinary situation (like e.g. during the coronavirus disease (COVID)-19 pandemic) limits or prevents on-site study visits, alternative methods of providing continuing care may be implemented. Phone calls, virtual contacts (e.g. teleconsult) or visits by site staff / home nursing service to the participant's home depending on local regulations and capabilities, can replace on-site study visits, for the duration of the extraordinary situation until it is safe for the participant to visit the site again. This also includes administration of study treatment by qualified study site personnel at a location other than the study site.

Table 8-1 Assessment Schedule

Period	Screening ¹	Part 1 (Double-blind, placebo-controlled)							Part 2 (Open-label, single-arm)				Follow-up
Visit Name	Screening	Day 1 (Baseline & 1st Treatment)	Day 30	Day 90	Day 150	Day 270	Day 330	Day 360 ("Switch Day") ²	Day 450	Day 510	Day 630	Day 720 (End of Treatment/ Study) ³	Safety follow-up (last visit +30 days) ⁴
Days	-28	1	30	90	150	270	330	360	450	510	630	720	750
Informed consent / assent (as applicable)	X												
Inclusion / Exclusion criteria	X												
Demography	X												
Pregnancy Test (serum) ⁵	X												
Pregnancy test (urine) ⁵		S						S				S	
Relevant medical history/current medical conditions	X												
Medical history Statin intolerance (if applicable)	X												
Smoking & Alcohol history	X												
Body weight / waist circumference	X	X	X	X	X	X	X	X	X	X	X	X	
Body Height	X	X			X		X			X		X	
Vital Signs ⁶	X	X	X	X	X	X	X	X	X	X	X	X	
Physical Exam (complete)	S						S					S	

Period	Screening ¹	Part 1 (Double-blind, placebo-controlled)							Part 2 (Open-label, single-arm)				Follow-up
Visit Name	Screening	Day 1 (Baseline & 1st Treatment)	Day 30	Day 90	Day 150	Day 270	Day 330	Day 360 ("Switch Day") ²	Day 450	Day 510	Day 630	Day 720 (End of Treatment/Study) ³	Safety follow-up (last visit +30 days) ⁴
Days	-28	1	30	90	150	270	330	360	450	510	630	720	750
Physical Exam (abbreviated)		S	S	S	S			S	S	S	S		
12-lead ECG	X						X					X	
Study drug administration ^{7,8}		X		X		X		X	X		X		
IRT call	X	X	X	X	X	X	X	X	X	X	X	X	
Prior/Concomitant lipid-lowering therapy	X	X	X	X	X	X	X	X	X	X	X	X	
(Other) Prior/Concomitant Medications	X	X	X	X	X	X	X	X	X	X	X	X	
Surgical/Medical Procedures	X	X	X	X	X	X	X	X	X	X	X	X	
LDL-apheresis recording (if applicable)	X	X	X	X	X	X	X	X	X	X	X	X	
Fasting LDL-C	X	X		X	X	X	X	X	X	X	X	X	
Fasting PCSK9		X		X	X		X	X		X		X	
Full fasting lipid / lipoprotein profile ⁹		X			X		X	X		X		X	
Anti-drug antibodies ¹⁰		X			X		X			X		X	
Full chemistry ¹¹		X					X					X	
Limited chemistry ¹¹	X		X	X	X	X		X	X	X	X		
Hematology	X	X	X		X		X		X	X		X	
Sexual hormones		X					X					X	
Urinalysis	X	X	X		X		X		X	X		X	

Period	Screening ¹	Part 1 (Double-blind, placebo-controlled)							Part 2 (Open-label, single-arm)				Follow-up
Visit Name	Screening	Day 1 (Baseline & 1st Treatment)	Day 30	Day 90	Day 150	Day 270	Day 330	Day 360 ("Switch Day") ²	Day 450	Day 510	Day 630	Day 720 (End of Treatment/Study) ³	Safety follow-up (last visit +30 days) ⁴
Days	-28	1	30	90	150	270	330	360	450	510	630	720	750

8.1 Screening

Screening activities ([Table 8-1](#)) must be initiated only after the ICF (and assent if applicable) has been signed.

It is not permissible to re-screen a participant if s/he fails the initial screening. In the case where a safety laboratory assessment at screening is outside of the range specified in the exclusion criteria, the assessment may be repeated once prior to randomization. If the repeat value remains outside of the specified ranges, the participant is not eligible for the study.

8.1.1 Information to be collected on screening failures

Participants for whom an ICF was signed and who are subsequently found to be ineligible prior to randomization will be considered a screen failure. The reason for screen failure should be recorded on an appropriate eCRF. The demographic information, informed consent, and inclusion/exclusion pages must also be completed for screen failure participants. If the screen failure participant experienced a SAE during the screening phase (see SAE section for reporting details), SAE information must additionally be collected. If the participant fails to be randomized, the IRT must be notified within 2 days of the screen fail that the participant was not randomized.

Participants who are randomized and fail to start treatment, e.g. participants randomized in error, will be considered an early terminator. The reason for early termination should be recorded on an appropriate eCRF.

8.2 Participant demographics/other baseline characteristics

Country-specific regulations should be considered for the collection of demographic and baseline characteristics in alignment with eCRF.

Participant demographic and baseline characteristic data to be collected on all participants include: age, sex, race, ethnicity, relevant medical history/current medical condition present before informed consent was signed (where possible, diagnoses and not symptoms will be recorded), concomitant lipid-lowering therapy, as well as relevant laboratory tests.

Investigators will have the discretion to record abnormal test findings as medical history in an appropriate eCRF whenever, in their judgment, the test abnormality occurred prior to the informed consent signature.

8.3 Efficacy

The efficacy assessments are specified below, with the Assessment Schedule ([Table 8-1](#)) detailing when each assessment is to be performed.

All efficacy biomarkers will be analyzed at a Central laboratory(ies). Participants will be in a fasted state for all efficacy laboratory assessments. At dosing visits, specimens for the analysis of efficacy biomarkers must be collected prior to study drug administration. Details regarding the collection, processing, shipping and storage of the samples will be provided in a Laboratory Manual. The Laboratory Manual will also provide details about prioritization when blood volume is restrictive ([Section 16.7](#) (Appendix 7)).

8.3.1 LDL-cholesterol

The primary efficacy assessment will be LDL-C. Samples for LDL-C will be collected at screening and on Days 1, 90, 150, 270, 330, 360, 450, 510, 630 and 720 ([Table 8-1](#)).

After randomization (Day 1) until the Day 360 visit, the results from the LDL-C laboratory assessments must be blinded to participants, investigator staff, persons performing the assessments, and the CTT.

In participants receiving LDL-apheresis, LDL-C must be measured immediately before the scheduled apheresis treatment.

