6.1.3 Treatment arms/group

Part 1 (Year 1):

Participants will be assigned at the baseline/randomization visit (Day 1) to one of the following two double-blind treatment groups in a 2:1 ratio:

- Inclisiran sodium 300 mg s.c.
- Corresponding placebo

Each participant will receive one injection of blinded inclisiran or placebo on Day 1, a second injection of blinded inclisiran or placebo on Day 90 and a subsequent injection of blinded inclisiran or placebo on Day 270 (“6 months dosing”).

Part 2 (Year 2):

Following a “Switch” Day (Day 360), all participants will receive the same active open-label inclisiran treatment:

- Inclisiran sodium 300 mg s.c.

Participants randomized to placebo in Part 1 will receive inclisiran sodium 300 mg s.c. starting on Day 360 (“Switch” Day 360). Participants randomized to inclisiran in Part 1 will receive placebo on Day 360. This dose of inclisiran/placebo on Day 360 will remain blinded in order to maintain the blind for Part 1 of the study.

All participants will receive subsequent doses of open-label inclisiran sodium 300 mg s.c. on Days 450 and 630.

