6.4 Treatment blinding

Part 1 (Year 1)

Part 1 of the study is randomized, double-blind and placebo-controlled. Participants, investigator staff, persons performing the assessments, and the clinical trial team (CTT) will remain blind to the identity of the treatment from the time of randomization until at least database lock for all Part 1 (Year 1) data, using the following methods: (1) Randomization data are kept strictly confidential until the time of unblinding, and will not be accessible by anyone else involved in the study with the following exceptions: the independent statistician and programmer who need to have access to prepare interim analysis reports for the DMC

[REDACTED]
These personnel will not be involved in any other trial activities. (2) The identity of the treatments will be concealed by the use of study treatment that are all identical in packaging, labeling, schedule of administration, and appearance.

Any [REDACTED] anti-drug antibodies and results from lipid/lipoprotein/PCSK9 measurements after the first administration of study drug until the Day 360 visit should be blinded for participants, investigator staff, persons performing the assessments and the CTT.

Unblinding will occur in the case of participant emergencies and at the conclusion of the study. Unblinding of the CTT and other parties (as needed) will also occur after the Year 1 database lock, which is planned after all participants have completed the Day 360 visit.

Part 2 (Year 2)

Due to the single-arm, open-label design, treatment in Part 2 of the study will be open to participants, investigator staff, persons performing the assessments, and the CTT.

In order to maintain the blind for Part 1 of the study, on the “switch” day (Day 360), participants randomized to placebo in Part 1 will receive blinded inclisiran, while participants randomized to inclisiran in Part 1 will receive blinded placebo.

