8.3.2 Other efficacy biomarkers

Other efficacy assessments will include:

- Apo B, Lp(a), non-HDL-C, total cholesterol, triglycerides, HDL-C, VLDL-C, Apo A1, PCSK9

Samples for these additional efficacy biomarkers will be collected on Days 1, 90 [REDACTED], 150, 330, 360, 510 and 720 ([Table 8-1](#)).

After randomization (Day 1) until the Day 360 visit, the results from the efficacy laboratory assessments must be blinded to participants, investigator staff, persons performing the assessments, and the CTT.

[REDACTED]

[REDACTED]

[REDACTED]

[REDACTED]

[REDACTED]

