8.4.1.1 Anti-drug antibodies

Serum samples for the analysis of formation of ADA will be collected at the time points detailed in the Assessment Schedule ([Table 8-1](#)).

On Day 1, ADA serum samples will be collected prior to injection and 4 hours after injection. At all other visits, one sample only will be collected.

The results from ADA after the first administration of study drug until the Day 360 visit must be blinded to participants, investigator staff, persons performing the assessments, and the CTT.

Instructions to be followed regarding sample collection, numbering, processing and shipment are outlined in a Laboratory Manual.

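### Protocol 8.3.1 and 8.3.2 mask lipid and PCSK9 results only until each participant's Day 360 visit, while 6.4 holds the Part 1 blind until the Year 1 database lock

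*Protocol*

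**What the plan says.** Two clocks govern the Part 1 blind.

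- **Treatment blind.** Protocol 6.4 keeps participants, site staff, assessors and the clinical trial team (CTT) blind "from the time of randomization until at least database lock for all Part 1 (Year 1) data". The same section plans that lock after all participants have completed Day 360, and puts the planned unblinding of the CTT after it.
- **Result masking.** For LDL-C, 8.3.1 says "After randomization (Day 1) until the Day 360 visit, the results from the LDL-C laboratory assessments must be blinded". For the other lipids and PCSK9, 8.3.2 says "After randomization (Day 1) until the Day 360 visit, the results from the efficacy laboratory assessments must be blinded to participants", and names the same groups as 6.4.

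Two further sections use the Day 360 limit with a different word order. Section 6.4 says that "anti-drug antibodies and results from lipid/lipoprotein/PCSK9 measurements after the first administration of study drug until the Day 360 visit should be blinded". Section 8.4.1.1 says "The results from ADA after the first administration of study drug until the Day 360 visit must be blinded to participants".

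The switch injection in 6.1.3 shows that the blind is meant to outlast a participant's own Day 360 visit: "This dose of inclisiran/placebo on Day 360 will remain blinded in order to maintain the blind for Part 1 of the study".

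**The concern.** Day 360 is a visit that each participant reaches on their own date; the Year 1 lock is one date for the whole trial. With about 12 participants, up to 11 can pass Day 360 before the last one does. For each of them, the masking duty in 8.3.1 and 8.3.2 lapses while the treatment blind in 6.4 is still running.

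The screening LDL-C predates the masking period and decides eligibility, so a site that receives later values can work out an approximate percent change. If that points to the arm, people who should be blind may know or guess allocation while judgements are still open:

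- Protocol 10.1.1 has the suspected relationship of an AE to study drug reassessed at each visit until the event resolves or is judged permanent. The causality of an ongoing Part 1 event can therefore change after Day 360.
- SAP 2.3.1 tabulates protocol deviations by category and Part.
- SAP 5.8 leaves the criteria for exclusion from analysis sets to be finalised before database lock.
- Protocol 12 requires the SAP to be final only before data lock.

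In so small a trial each such decision carries weight.

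**Working it through.** **Step 1. The end points side by side**

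| Place | What is masked | Stated limit | What the limit attaches to |
|---|---|---|---|
| 6.4, opening rule | Treatment identity | Year 1 lock, at least | The blinding |
| 8.3.1 | LDL-C | Day 360 visit | The blinding |
| 8.3.2 | Other lipids, PCSK9 | Day 360 visit | The blinding |
| 6.4, results sentence | Lipids, PCSK9, ADA | Day 360 visit | Blinding, or the samples covered |
| 8.4.1.1 | ADA | Day 360 visit | Blinding, or the samples covered |

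In 8.3.1 and 8.3.2 the time phrase opens the sentence and governs the duty to blind. In 6.4 and 8.4.1.1 it follows the results or measurements, so it can equally define which samples are masked. Two sections therefore clearly state the shorter period.

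**Step 2. The gap**

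For one participant it runs from their own Day 360 visit to the last participant's Day 360 visit, plus the time from then to lock. Neither the accrual period nor the interval to lock is given, so its length cannot be computed.

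**Step 3. The Day 360 sample**

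Protocol 8.3 requires efficacy specimens at dosing visits to be drawn before the injection. The Day 360 sample therefore reflects Part 1 treatment only. The stated limit does not say whether this sample is inside the masking.

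**Step 4. How informative one LDL-C value could be**

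The plan has no figure to reproduce: Protocol 12.8 and SAP 3 base the sample size on feasibility and give no effect or SD. The placebo-adjusted reductions of 48% to 52% in Protocol 4.2 come from adults with ASCVD, risk equivalents or HeFH, not HoFH. Both inputs are therefore assumed and varied.

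Let percent change be normal with common SD s, mean 0 on placebo and −d on inclisiran, and let the prior be 2/3 inclisiran (2:1). The best rule calls inclisiran when the value is below c:

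- c = −d/2 + (s²/d) × ln 2
- P(correct) = 2/3 × Φ((c + d)/s) + 1/3 × [1 − Φ(c/s)]

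Lowest case, d = 15, s = 30: c = −7.5 + 60 × 0.693 = 34.1. P = 2/3 × Φ(1.636) + 1/3 × [1 − Φ(1.136)] = 0.633 + 0.043 = 0.675.

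Highest case, d = 50, s = 10: c = −25 + 2 × 0.693 = −23.6. P = 2/3 × Φ(2.639) + 1/3 × Φ(2.361) = 0.664 + 0.330 = 0.994.

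| Assumed effect d (points) | SD 10 | SD 15 | SD 20 | SD 30 |
|---|---|---|---|---|
| 15 | 79.6% | 73.0% | 69.9% | 67.5% |
| 20 | 85.5% | 77.4% | 73.0% | 69.0% |
| 30 | 93.8% | 85.5% | 79.6% | 73.0% |
| 40 | 97.9% | 91.6% | 85.5% | 77.4% |
| 50 | 99.4% | 95.6% | 90.3% | 81.7% |

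The benchmark is 2/3 = 66.7%, from always guessing inclisiran. One value thus runs from almost no information to near certainty. Section 8.3.1 schedules five Part 1 LDL-C samples after the first dose (Days 90, 150, 270, 330 and 360). What they add together depends on their within-participant correlation, which is not given, so it is not computed.

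**The case against.** The strongest reply is that no release is prescribed. Section 6.4 is the blinding section, and its duty to keep everyone blind until the lock can be read as barring release of any result that would show allocation. Reporting of results by the central laboratory is set out in the Laboratory Manual (8.4.1), which is not among these documents, and parts of 6.4 are redacted. The Day 360 limit also has an innocent purpose as a sample window, since LDL-C is flagged to sites from Day 450 (6.5.1).

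Much of this stands. A reader might infer that the protocol unblinds each participant at Day 360; it does not, because it only stops requiring that results be withheld. A reader might also count 6.4 and 8.4.1.1 as clear statements of the shorter period, but their wording allows the sample-window reading. ADA results are unlikely to disclose much, since Protocol 1.1 describes the potential for immunogenicity as low.

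The reply does not remove the conflict in 8.3.1 and 8.3.2. There the time limit applies to the blinding, and a laboratory or site following those sections literally may release results before the lock. Section 6.4 states the aim but not that these results are withheld until then.

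**Conclusion.** The conflict between 8.3.1 and 8.3.2 on one side and 6.4 on the other is real and worth an amendment. It permits early disclosure; the documents do not show that disclosure occurs.

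A reader might go further and conclude that the primary endpoint is biased. That is not supported: by a participant's Day 360 visit the Day 330 sample has been drawn, and it is assayed centrally. No hypothesis test is planned either. What is exposed is the judgement around the data, namely causality of ongoing AEs, deviations and analysis-set exclusions, and only if results reach blinded staff before the lock.

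Nor can one say that a released value identifies the arm. The range of about 67.5% to 99%, against 66.7% by guessing, rests on assumed effects of 15 to 50 points, SDs of 10 to 30, normality and 2:1 allocation. The HoFH effect and the SD are not in the documents. The length of the exposure is unknown as well.

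**What to change.** - **8.3.1 and 8.3.2:** state that results from all samples taken after the first dose, up to and including the Day 360 pre-dose sample, stay withheld from participants, site staff, assessors and the CTT until the Year 1 database lock.
- **6.4 and 8.4.1.1:** keep the Day 360 phrase as the sample window and add that these results stay withheld until that lock. Simply replacing the Day 360 phrase with the lock date would, on the sample-window reading, mask early participants' Part 2 samples and collide with the 6.5.1 flag.
- **Part 2 results available before the lock:** state how they are handled, and reconcile that with the LDL-C flag from Day 450 onward in 6.5.1. Both arms are scheduled to have had inclisiran by then, so these results should be less revealing.
- **Laboratory Manual:** align its reporting instructions.
- **If any Part 1 results have already been released before the lock:** report when and to whom.

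The cost is wording, plus later sight of Part 1 lipid values for sites. No planned analysis changes.
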